## c. Statistical plan including sample size justification and interim data analysis.

Design. This is a crossover trial, where each participant will be randomly assigned to receive either "IFG tDCS, then sham then SMG (in case a second stimulation site is implemented)" (group1) or "SMG then sham then IFG" or "sham then IFG then SMG". In case a second stimulation site is not implemented participants will receive either sham and then tDCS (group 1) or tDCS and then sham (group 2). Based on previous studies regarding long-term effects of tDCS (see Fiori et al., 2011; Fridriksson et al., 2011; both looking at 3-weeks post-stimulation in participants with aphasia) and given the degenerative nature of PPA (and some cases of MCI), we assume that even though the effect of tDCS on the absolute level of the outcome may or may not persist at 2 weeks, the effect on the rate of decline persists no longer than 2 weeks. Analyses. The primary analyses will be a robust type of repeated measures Multivariate ANCOVA. Specifically, for each subject (i) and at follow-up times t=immediately after treatment, then 2 weeks and 2 months, we will consider the data  $IFG_{ti}$ ,  $SMG_{ti}$ , and  $S_{ti}$ ; here,  $IFG_{ti}$  is the change of outcome from just before IFG tDCS treatment to time t after IFG tDCS treatment for subject i; and similarly for SMGt,i, and St,i for IFG tDCS and sham. For the behavioral methods, change of outcome is considered the difference (before and after therapy) of the independent measure of initial letter-sound associations learned. Then the research hypothesis that IFG (or SMG) treatment is superior to sham will be tested by testing the hypotheses that the distribution  $pr(R_{ij} - S_{t,i})$  (or  $pr(L_{t,i} - S_{t,i})$ ) is not centered at zero. This will be done nonparametrically by obtaining the latter null distributions by the random permutation of the treatment labels (IFG, S, SMG) of the data for each patient (Rosenbaum, 1988). The design effect, i.e., the ratio of sample sizes needed by an independence design vs. the crossover design to achieve a given power, depends on the correlations of outcomes across times and treatments. We have calculated that this crossover design with 30 participants and design effect of 1.5 has power 75% to detect an effect size of 0.8 between a tDCS site and sham treatment. In secondary analysis, we will use regression to examine if any effects of tDCS vary across participants with different characteristics such as age and atrophy volume. The present design allows us to evaluate the language and neuromodulatory effects of both IFG and SMG stimulation as well as language therapy alone (in the condition of sham stimulation).

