conditioning using tDCS have received Johns Hopkins IRB approval. We will use either the same equipment as [name] and his team have used (a Chattanooga lonto Device) as well as the same application technique, recently acquired state-of-the-art device using special software for doubleblinding (Soterix 1x1 CT: clinical trials), or a Neuroelectrics Starstim 8 device, which is a high-definition tDCS cap with higher precision. In order to administer intervention during the global pandemic and in a virtual manner, we will offer the option of remote stimulation (Soterix mini-CT device and MIND STIM+, YBrain). Attached please find letters from Clinical Engineering documenting that the tDCS devices have undergone clinical inspection as well as the manuals. When remote devices are implemented, participants and spouses will be trained prior to intervention and sessions will be conducted in real-time via video conference (e.g., Zoom). Stimulation will be delivered at an intensity of 1-2mA (estimated current density 0.04 mA/cm2; estimated total charge 0.048C/cm2) for a maximum of 20 minutes in the tDCS groups and for a maximum of 30 seconds in the Sham group. For both interventions (tDCS and Sham) the electrical current will be increased in a ramp-like fashion at the onset of the stimulation eliciting a transient tingling sensation on the scalp that usually disappears over seconds. Although the ramping process requires the researcher's input, it is now feasible to blind study staff who will be applying tDCS, as well as participants, as we now have a box that allows another member of the team to set the box to "tDCS" or "sham" without the knowledge of the researcher providing the therapy. In the Starstim 8 and remote devices, double-blinding is achieved through codes known only to the PI who is not administering any stimulation or evaluation, so both the technician or professional who administers the stimulation and evaluation are blind to the current condition being either actual tDCS or sham. After the ramping, in the sham condition, the intensity drops to 0 mA. These procedures have been shown to successfully blind participants as to whether they were members of experimental or control groups (Gandiga et al., 2006). The sites of tDCS application will be determined by the type of therapy used and the PPA variant group or MCI and will be either the inferior frontal gyrus (IFG), the supramarginal gyrus (SMG), or the middle temporal gyrus (MTG) or a combination as shown in the literature. A recent meta-analysis of the functional neuroimaging literature on spelling has not yet identified clearly the neural substrates for PG conversion; the most plausible network includes the inferior parietal lobule including the supramarginal gyrus (Purcell et al., 2011). This area has also been identified as a critical area for spelling in the lesion literature as well. Another plausible area that shows activations during both PG conversion and lexical (word) spelling is the inferior frontal gyrus (IFG) (Purcell et al., 2011) and lesions in the IFG are associated with impaired PG conversion (Beeson et al., 2010). The stimulation site of IFG will be determined between F7 and F8 electrodes and that of SMG between TP3 and TP4 using the EEG 10-20 electrode position system (Homan, 1988). Additionally, studies have reported positive results of tDCS over the left dorsolateral prefrontal cortex (DLPFC) leading to improvement in attention deficits due to stroke, Parkinson's disease, and major depression (Boggio et al., 2006, 2007; Fregni et al., 2006; Kang et al., 2009). In addition to improving attention, anodal tDCS at the left DLPFC has been shown to improve working memory in TBI patients (Ulam et al., 2015). We hypothesize that anodal tDCS over the L DLPFC when administered in combination with cognitive training will improve language performance of PPA and MCI participants more than behavioral therapy alone, and that improvements may generalize to some other cognitive functions. The dependent variable will be the same baseline and post-therapy evaluation as described above that will take place before, after, 2 weeks and 2 months post-stimulation for each stimulation condition (see Table 1). These same areas, predominantly on the left, are activated during naming (Jarso et al., 2013) and working memory (Philipose et al., 2007). In most cases of PPA and all cases of MCI, we will stimulate areas of the left hemisphere that are not atrophied. In the most advanced cases of PPA, with severe left hemisphere atrophy, we will stimulate the same sites in the right hemisphere in order to stimulate its compensatory mechanisms (see Hypothesis 1d). By this design we will be able to achieve a within-subject design for all conditions as well as to evaluate immediate, short- and long-term effects of each stimulation site without confounds and without any carry-over effects. We will also conduct a 6-month language evaluation to assess the overall therapy gains.

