## b. Study duration and number of study visits required of research participants.

Before any intervention participants will be enrolled in a control condition for 12 weeks during which no therapy will be provided to enable us to assess their personal decline rate. After this period they will be randomly assigned to either sham or tDCS experimental conditions. Three pre-training sessions may be proposed to test the tDCS experimental conditions before training. After 1-3 weeks of tDCS application (3-5 sessions in a week, 5-15 sessions per stimulation site) there will be an interval of approximately 2 months and then we will implement the other two tDCS conditions in a within-subject cross-over design, an example of which is shown in Table1. We will follow-up the participants with 2-week, 2-month and a final 6-month follow-up sessions. For those participants who are long-distance, at the 2-week time point we may use a video conferencing tool such as GoToMeeting to administer the assessments. This is to mitigate the costs of travel for a short appointment. In these sessions we will administer the behavioral therapy assessment as described in the therapy section. We will test participants with both the practiced items and unpracticed items to look at generalization effects to untrained items. Given that we will test each participant in different conditions, an example of the sequence of conditions is shown in Table 1. After the final evaluation of interventions, we will offer an optional remote extension phase. This will consist of 18 additional months of intervention: 50 therapy sessions+tDCS (in 10 weeks) every 3 approximately months for a 18-month period, depending on availability, using different areas of stimulation (either the IFG, SMG, MTG, or DLPFC or Precuneus based on previous literature, see above in tDCS methods for details) for up to 18 months in total. We will complete another full evaluation of language and cognitive skills at the end of the stimulation phase. We will compare maintenance of therapy gains for individuals who participate in these remote sessions to those who do not, to answer the question whether tDCS effects may be extended beyond the initial 2-month period follow-up, up to 18 months and whether the rate of decline may change. This is very important because long periods of interventions and followup are needed in studying intervention outcomes in a neurodegenerative disorder.

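### If the second stimulation site is used, the three listed orders tie treatment to period (sham never third, SMG third in two of three), and the stated permutation test has no period term

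*Combined protocol and SAP*

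**What the plan says.** Section 6c (statistical plan) describes a crossover in which "each participant will be randomly assigned to receive either" one of three orders if a second site is used:

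- "IFG tDCS, then sham then SMG (in case a second stimulation site is implemented"
- "SMG then sham then IFG"
- "sham then IFG then SMG"

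Without a second site there are two orders, sham then tDCS or the reverse, as in Table 1. No allocation ratio is given for either version.

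The outcome in each period is the change from just before that period's treatment. The primary analysis is called a robust repeated measures multivariate ANCOVA, with no covariates listed. It is then specified as a test that the within-patient difference between site and sham is centred at zero, with the null distribution obtained by "random permutation of the treatment labels (IFG, S, SMG) of the data for each patient". No period or sequence term is mentioned.

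Section 6c adds that "The present design allows us to evaluate the language and neuromodulatory effects of both IFG and SMG stimulation". The tDCS methods in Section 3a say the design gives the "effects of each stimulation site without confounds and without any carry-over effects".

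**The concern.** In a crossover, a simple within-patient difference is free of period effects only if each condition falls equally often in each period. The three listed orders do not achieve that. Each condition is first once, but in the other two orders sham is always second, while SMG is always third in the orders where it is not first.

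Anything that makes the expected gain in period 3 differ from that in period 2 then enters the comparison with sham. Candidates are accelerating decline, waning response to therapy, continued learning, or differences between the item sets used in successive periods. Permuting labels within a patient treats the three periods as exchangeable, so the test inherits the bias.

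At stake is the claim that both sites can be evaluated without confounding. If gains fall over the periods, the main harm is lost power for SMG. If they rise, the bias favours tDCS.

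**Working it through.** **1. The plan's own power figure.** Section 6c gives 30 participants, design effect 1.5, effect size 0.8 and power 75%. Then 30 × 1.5 = 45 independent participants, or 22.5 per arm, and 0.8 × √(22.5/2) = 2.68. At two-sided 5% (assumed; alpha is not stated) power is 76.5% by the normal approximation and 74.6% by noncentral t, so the figure reproduces. The implied SD of a within-patient difference is √30 × √(2/22.5) = 1.63, used below as the calibrated setting.

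**2. Period positions**

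| Order | IFG | SMG | Sham |
|---|---|---|---|
| IFG, sham, SMG | 1 | 3 | 2 |
| SMG, sham, IFG | 3 | 1 | 2 |
| Sham, IFG, SMG | 2 | 3 | 1 |

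**3. Bias.** Let p1, p2, p3 be the expected change scores by period apart from treatment. With equal allocation the period contributions to the condition means are:

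- Sham: (p1 + 2p2)/3
- IFG: (p1 + p2 + p3)/3
- SMG: (p1 + 2p3)/3

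Hence SMG minus sham is biased by 2(p3 − p2)/3 and IFG minus sham by (p3 − p2)/3. p1 cancels, so an effect confined to the first period does no harm. Because outcomes are change scores, steady decline also cancels. The one-half relation needs equal allocation: at 0.4/0.3/0.3 the SMG bias is 0.7(p3 − p2) and the IFG bias is 0.1p1 − 0.4p2 + 0.3p3.

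**4. Effect on the stated test.** The documents give no drift, so these sizes are assumptions: 30 participants, 10 per order, linear drift per period, two-sided 5%. The variance settings are SD 1 with within-patient correlation 0, SD 1 with correlation 0.5, and the calibrated setting, shown in that order. Power is for a true effect of 0.8 at both sites.

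| Drift per period | SMG bias | SMG type I error, % | SMG power, % |
|---|---|---|---|
| 0 | 0 | 5.0 / 5.0 / 5.0 | 84 / 99 / 74 |
| −0.1 | −0.07 | 6.3 / 6.2 / 5.6 | 77 / 97 / 65 |
| −0.25 | −0.17 | 9.3 / 12.7 / 8.2 | 63 / 89 / 51 |
| −0.5 | −0.33 | 18.2 / 28.5 / 14.9 | 33 / 53 / 27 |

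Simulations used 4,000 trials and 999 permutations, except the −0.1 row and the correlation-0.5 powers (1,500 to 8,000 trials, 499 permutations).

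- IFG type I error stays at 5.1–7.2% for drifts of −0.25 and −0.5. Its calibrated power falls from 74% to 49% at −0.5.
- At −0.5, false rejections favouring tDCS are 0.3% or less. At +0.5, 14–27% of null SMG tests falsely favour tDCS.
- With period effects (0, −0.5, −0.5), so that p2 = p3, bias is 0 and type I error is 3–5%.

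**5. Can the three orders be rescued in analysis?** A least-squares fit with subject, period and treatment gives zero bias under a pure period effect. In units of within-patient variance, the variance of SMG minus sham is 0.120 and of IFG minus sham 0.080, against 0.067 for period-balanced orders. The ratios are 1.8 and 1.2.

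Subtracting raw period means instead would be wrong, because the periods hold unequal mixes of conditions. With true effect d at both sites the period means are 2d/3, d/3 and d. The average period mean removed is 8d/9 for SMG, 2d/3 for IFG and 4d/9 for sham. SMG minus sham becomes (d − 8d/9) − (0 − 4d/9) = 5d/9, and IFG minus sham becomes (d − 2d/3) + 4d/9 = 7d/9.

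**The case against.** The strongest reply is that this is an optional branch with an undocumented effect. The design described in Section 3a (Analyses) and in Table 1 has one site, and it is balanced at 1:1. Section 3b does say "then we will implement the other two tDCS conditions in a within-subject cross-over design", but it cites Table 1 as the example, so it does not show that the three-order version is in use. This stands: the point applies only if a second site is implemented.

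The size also rests on assumed drifts. A drift of 0.5 is more than 60% of the 0.8 design effect (0.5/0.8 = 0.63), and outcomes are already change scores. At 0.1 per period the type I error is about 6% and calibrated power falls from 74% to 65%. The word sets for lexical therapy are matched on four properties, which limits item-set differences, and that text covers only two conditions. Nothing in the documents shows that p3 differs from p2. This too stands, but nothing argues that they are equal either. The plan's statements on carry-over and persistence do not address period effects.

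Two readings of the analysis might soften the point. The ANCOVA could contain an unlisted period term, but the text goes on to define it by the permutation test and names none. Alternatively, the permutation could re-draw only the three randomised orders. With its null distribution recentred, that test held 4.5–6.2%, but the estimated differences stayed biased, and the text describes permuting labels within each patient. Permuting over all six label orders is not itself an error: with no period effect it holds 5%.

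**Conclusion.** The concern holds for the two-site option. The imbalance follows exactly from the listed orders. Under equal allocation and additive period effects, the bias is 2(p3 − p2)/3 for SMG minus sham and half that for IFG minus sham. Neither the design nor the stated test removes it, so the claim of unconfounded evaluation of each site requires p2 = p3, which the plan neither states nor justifies.

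The practical size is uncertain because the drift is unknown: negligible near zero, minor at 0.1 per period, and serious for SMG at 0.25 to 0.5. Downward drift mostly costs power; upward drift produces false findings for tDCS. It should be fixed before the two-site option is used. The one-site design needs no change on this ground if allocated 1:1.

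**What to change.** **If a second site is used:** randomise to all six orders of IFG, SMG and sham (5 per order at 30 participants) or another period-balanced set, and state the allocation ratio. Put a period term in the analysis, and build the null distribution by re-randomising order assignments between participants. In simulation the six-order version gave zero bias and type I error of 4.5–5.5%. At a drift of −0.5, SMG power was 85% (SD 1, correlation 0) and 74% (calibrated).

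**For anyone already allocated to the three orders:** fit subject, period and treatment jointly and re-randomise over those three orders. Do not subtract raw period means. This gave zero bias and type I error of 4.5–5.4%, but SMG power was 59% and 47%, and IFG power 77% and 66%, in the same two settings.

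**Cost:** a new randomisation list for the two-site option, a few lines of analysis text and two degrees of freedom for period, with no extra participants or visits. Keeping the three orders and adjusting only the analysis costs more: matching the SMG precision of 30 participants on six orders would take 30 × 1.8 = 54.

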#### c. Blinding, including justification for blinding or not blinding the trial, if applicable.

Participants will be blinded to the application of anodal or sham tDCS. To achieve blinding, all participants will be fitted with the tDCS electrodes placed over the appropriate stimulation sites. As individuals typically experience a mild tingling sensation following the initiation of stimulation, both active and sham conditions will involve a ramping up of the current to appropriate intensity (1-2 mA) over 10-15 seconds to allow participants to habituate to the tingling sensation. At this point, the current will be ramped back down to 0 mA for individuals in the sham condition. Termination of the stimulation after the ramping up process is generally undetectable, and the brief duration of stimulation yields no functional effects. Staff who will be applying tDCS will also be blinded to the sham vs tDCS treatment condition.

d. Justification of why participants will not receive routine care or will have current therapy stopped

Participation in this study will not disrupt any current care or therapy.

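### If a second stimulation site is used, sham is never the third block, so the blinding promised in sections 3a and 3c is only partial in that version

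*Combined protocol and SAP*

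**What the plan says.** Section 6c gives the two-site version three blocks: active IFG, active SMG and a single sham. Three orders are allowed: "IFG tDCS, then sham then SMG (in case a second stimulation site is implemented", "SMG then sham then IFG" and "sham then IFG then SMG". If there is no second site, participants have two blocks, sham and tDCS, and both orders are used.

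The two sites lie at different places on the scalp. Section 3a (tDCS methods) states: "The stimulation site of IFG will be determined between F7 and F8 electrodes and that of SMG between TP3 and TP4".

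Blinding is promised without qualification. Section 3c says that participants are blinded and adds: "Staff who will be applying tDCS will also be blinded to the sham vs tDCS treatment condition". It also says that "all participants will be fitted with the tDCS electrodes placed over the appropriate stimulation sites", but not which site is the appropriate one for a sham block that serves two sites. For the cap and the remote devices, section 3a says that "both the technician or professional who administers the stimulation and evaluation are blind to the current condition". The means described are current ramping, a box pre-set by another team member, and codes held by the principal investigator.

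**The concern.** The blinding measures hide whether current flows. They do not hide which block a participant has reached or where the electrodes are placed. In the two-site version both carry information about the condition, because sham never comes last and because one sham block has to serve two sites.

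The outcomes in section 6a are percent-correct scores on therapy items, and in the naming and repetition therapies the therapist gives cues or models and judges responses. Someone who knows that a block is active may cue, encourage or score differently. In block 3 that certainty can fall only on active stimulation, so any expectation effect there favours tDCS over sham. Permuting treatment labels within each patient, as section 6c plans, would not remove this, and neither would a period term, because the effect follows knowledge of the condition.

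**Working it through.** **The plan's own figure.** Section 6c gives no figure for blinding. Its only figure is 75% power for effect size 0.8 with 30 participants and design effect 1.5. Taking 30 × 1.5 / 2 = 22.5 per group and two-sided alpha 0.05 (assumed, as alpha is not stated), power is 0.746 (t-based) or 0.765 (normal). The figure reproduces, and nothing below depends on it.

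**Inputs.** The three orders come from section 6c: O1 = IFG-sham-SMG, O2 = SMG-sham-IFG, O3 = sham-IFG-SMG. Assumptions: equal allocation to orders, an observer who knows the list, and a visible electrode site. The sham site is not stated, so each possibility is tried.

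**Rule.** At each fitting, keep the orders that match the sites seen so far. The block's status is certain if it is sham in all of them or in none. The share is certain blocks / all blocks.

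**Position only (site hidden).** Block 1 is sham in 1 of 3 orders, block 2 in 2 of 3, block 3 in 0 of 3. Only block 3 is certain: 3/9.

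**Sham at IFG.** Visible sites are O1: IFG-IFG-SMG; O2: SMG-IFG-IFG; O3: IFG-IFG-SMG.
- Block 1: a start at SMG means O2, so active (1 certain of 3).
- Block 2: in O2 it must be sham (1 of 3).
- Block 3: always active (3 of 3).
- Share: (1 + 1 + 3)/9 = 5/9 = 56%. O1 and O3 look the same, so IFG versus sham stays at 50:50 in their blocks 1 and 2.

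**Sham at SMG.** Visible sites are O1: IFG-SMG-SMG; O2: SMG-SMG-IFG; O3: SMG-IFG-SMG.
- Block 1: a start at IFG means O1, so active (1 of 3).
- Block 2: the first two sites identify the order (3 of 3).
- Block 3: always active (3 of 3).
- Share: (1 + 3 + 3)/9 = 7/9 = 78%.

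**Sham site random (50:50).** There are 3 × 2 = 6 equally likely combinations.
- Block 1: sham in 1/3 of cases at either site (0 of 6 certain).
- Block 2: IFG-SMG and SMG-SMG each make block 2 certainly sham (2 of 6); IFG-IFG and SMG-IFG leave it at 1/2.
- Block 3: 6 of 6.
- Share: (0 + 2 + 6)/18 = 4/9 = 44%.

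**All six orders.** With a fixed sham site the share is 3/9. With a random sham site there are 12 combinations:
- Block 1: 0 of 12 certain.
- Block 2: 0 of 12 certain.
- Block 3: certain only after two blocks at the same site, that is IFG-IFG-SMG or SMG-SMG-IFG (4 of 12), and always active.
- Share: 4/36 = 1/9 = 11% overall, and 4/12 = 1/3 of third blocks.

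| Scheme | Block 1 | Block 2 | Block 3 | Overall |
|---|---|---|---|---|
| Three orders, sham at IFG | 1/3 | 1/3 | 1 | 5/9 |
| Three orders, sham at SMG | 1/3 | 1 | 1 | 7/9 |
| Three orders, random sham site | 0 | 1/3 | 1 | 4/9 |
| Six orders, random sham site | 0 | 0 | 1/3 | 1/9 |

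In every scheme with sham at IFG or SMG, the site used only once is known to be active by the end of block 3, because the single sham block shares the other site.

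**The case against.** The case against has real weight.

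- **The version is conditional.** Section 3 (Analyses) names control, IFG tDCS and sham, and Table 1 shows one 15-session sham block and one 15-session LIFG block in both orders. There sham and active can share a site and the problem does not arise. This limits the scope but does not make the point empty: the primary analysis in section 6c is written for IFG, SMG and sham.
- **Knowledge of the order list is assumed.** The documents do not say who has it. This stands, most strongly for participants.
- **The site may not be visible.** A multi-electrode cap set up identically in every block could hide it. This stands for that device, one of several allowed, but block 3 would still be known from its position.
- **The evaluator may not see the electrodes.** An evaluator who does not fit them learns only what block position reveals. This also stands.

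A reader might infer that staff and participants can work out every block. The documents do not support that. With sham at IFG, two of the three orders look identical and IFG versus sham stays masked in their first two blocks. Full identification of all three orders would need, for example, sham always at SMG, which is not stated.

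**Conclusion.** The concern holds in a limited form. In the two-site version block 3 is always active, and someone who knows the order list knows this whatever the device or site. Where the site is also visible, between 4/9 and 7/9 of blocks have certain status at fitting in the scenarios tried. Those shares rest on equal allocation, knowledge of the list and an assumed sham site. The unqualified blinding statements in sections 3a and 3c therefore do not hold for this version.

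It would go too far to conclude that blinding fails across the trial or that its results are biased by a known amount. The one-site version is unaffected, the documents do not say how many participants would have two sites, and the size of any expectation effect cannot be estimated from them. Only its direction in block 3, towards tDCS, follows from the design.

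**What to change.** In section 6c, for the two-site version only, randomise to all six orders of IFG, SMG and sham. Draw the electrode site of the sham block (IFG or SMG) at random for each participant. Hold both in the existing code system, so that the person fitting the electrodes is told the site but not the condition.

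Both changes are needed: six orders with a fixed sham site still leave 3/9 of blocks certain, against 1/9 with a random one. Even together they reduce the problem without removing it, since third blocks can still be identified as active after two blocks at one site. Sections 3a and 3c should therefore say that blinding is partial when two sites are used.

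The cost is a longer code list and a short protocol edit, with no added visits, staff or participants. The downside is small: if all 30 participants were in the two-site version, there would be about 30/6 = 5 per order instead of 30/3 = 10, and sham fittings would be split between the two sites.

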#### 6. Study Statistics

#### *a. Primary outcome variable.*

The primary outcome measures will be: a) change in performance from pre- to post-treatment levels on the trained items (e.g. change in % accuracy in phoneme-grapheme conversion of trained phonemes, % accuracy naming of trained pictures, average % correct names produced in trained categories in 1 minute), and, b) generalization to untrained items, measured by change in performance from pre- to post-treatment levels on the trained items (e.g. change in % accuracy in phoneme-grapheme conversion of untrained phonemes, % accuracy naming of untrained pictures, average % correct names produced in untrained categories in 1 minute). For those individuals with DLPFC stimulation for executive functions, we will use an additional automated score from BrainHQ program training (Smith et al., 2009). For individuals

receiving home-based tDCS over the left perisylvian areas and their right hemisphere homologs, we will assess pre- to post- language scores.

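### Two unranked primary outcomes, one or two sites and three times are tested with no primary contrast, alpha, success rule or multiplicity control

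*Combined protocol and SAP*

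**What the plan says.** Section 6a (Primary outcome variable) lists two measures: "The primary outcome measures will be: a) change in performance from pre- to post-treatment levels on the trained items", and "b) generalization to untrained items". They are joined by a plain conjunction. The section does not rank them or say whether one or both must succeed. It adds further measures for participants with DLPFC stimulation and for home-based participants; these are not counted below.

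Section 6c (Statistical plan) describes the primary analysis as a robust form of repeated-measures multivariate ANCOVA, using change scores "immediately after treatment, then 2 weeks and 2 months". The hypothesis that "IFG (or SMG) treatment is superior to sham" is tested by asking whether the within-patient difference from sham "is not centered at zero", with the null distribution obtained by permuting treatment labels within each patient. The use of a second site is conditional. The Analyses text in section 3 and Table 1 in section 3b show one active treatment site, IFG, plus sham.

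The power statement in section 6c is for one tDCS site against sham: 30 participants, design effect 1.5, effect size 0.8, power 75%. No significance level is given there or elsewhere.

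**The concern.** The plan allows several primary comparisons and does not say which one decides the trial. If each is judged at the usual level and any one can support superiority, the chance of at least one false positive exceeds the nominal level. The choice of outcome, site and time to present as the main result could also be made after the data are seen.

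The power statement has a matching problem. It describes one comparison, so it does not describe the chance of success for a family of tests, or for any one test once multiplicity is controlled.

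**Working it through.** **1. Reproduce the stated power.** Inputs from section 6c: 30 participants, design effect 1.5, effect size 0.8. The equivalent independent sample is 30 × 1.5 = 45, or 22.5 per arm. The noncentrality is 0.8 × √(22.5/2) = 2.68 on 2 × 22.5 − 2 = 43 degrees of freedom.
- Two-sided 5%: noncentral t 74.6%, normal approximation 76.5%. This matches 75%.
- One-sided 5%: 84-85%. No match.
- Two-sided 2.5%, as Bonferroni over two tests would need: 64-67%. No match.

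So 75% fits one unadjusted two-sided 5% test. The 5% used below is inferred from this fit and is otherwise an assumption.

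**2. Count the tests that the text permits.**
- One site, one time or one joint test over times: 2 outcomes × 1 × 1 = 2.
- One site, each time separately: 2 × 1 × 3 = 6.
- Two sites, one time or one joint test: 2 × 2 × 1 = 4.
- Two sites, each time separately: 2 × 2 × 3 = 12.

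**3. Chance of at least one false positive at 5% two-sided per test, any one success counting.** The plan gives no correlations. I assumed 0 to 0.8 between outcomes and between times. I assumed 0.5 between the two site contrasts, because both subtract the same sham data (equal variances assumed). For k independent tests the rate is 1 − 0.95^k. For two correlated tests it is 0.05 + 0.05 − P(both reject). The other correlated cases were simulated from a multivariate normal distribution.

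| Tests | Correlation 0 | 0.5 | 0.8 |
|---|---|---|---|
| 2 (one site) | 9.8% | 9.1% | 7.8% |
| 6 (one site, three times) | 26.5% | 22% | 15% |
| 4 (two sites) | 17% | 16% | 14% |
| 12 (two sites, three times) | 43% | 37% | 26% |

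Columns give the correlation across outcomes and, where times are tested separately, across times; the site correlation stays at 0.5. For two tests, P(both reject) is 0.0025 at correlation 0, 0.0093 at 0.5 and 0.0219 at 0.8, so the rates are 0.10 − 0.0025 = 0.0975, 0.10 − 0.0093 = 0.0907 and 0.10 − 0.0219 = 0.0781.

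**4. False claims in favour of tDCS only.** Each two-sided 5% test rejects in that direction 2.5% of the time. Over the same correlation range the rates are about 4-5% (2 tests), 7-14% (6 tests) and 13-24% (12 tests), against 2.5% for a single test.

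**5. Power if Bonferroni were used instead.** With the noncentral t and the inputs of step 1, power for one contrast is 64% over 2 tests, 47% over 6 and 38% over 12. This shows how far the 75% depends on there being one test. Bonferroni is not the remedy proposed here.

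**The case against.** The best defence is that the family may be much smaller than 12.
- SMG is conditional, and the design shown in section 3 has one active treatment site.
- A repeated-measures multivariate method can naturally be read as one joint test over times, and section 6a defines both outcomes as pre- to post-treatment change, which may mean a single time.
- Section 6c mentions one behavioral change score, the "change of outcome is considered the difference (before and after therapy) of the independent measure of initial letter-sound associations learned", though it does not say which of the two primary outcomes this is.
- If both outcomes had to succeed, the second outcome would add no error.

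All of this stands as a limit on the size of the problem. None of it removes the problem, because the plan does not commit to any of these readings. Even with one site and one test over time, the error is close to double the nominal 5% if either outcome can succeed.

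A reader might infer that the plan runs 12 primary tests with a 46% error rate (1 − 0.95^12 = 0.46). The documents do not support that. Twelve is a maximum, and 46% requires independence, which the shared sham condition rules out. A reader might also take these rates as the chance of wrongly declaring a tDCS benefit. They count rejections in either direction, so that chance is about half as large.

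**Conclusion.** The gap is real. Two unranked primary outcomes, one or two site contrasts and data at three times are left without a primary contrast, alpha, success rule or multiplicity control, and the 75% power applies to one unadjusted two-sided 5% test.

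The family-wise error is about 8-10% for 2 tests (9-10% for correlations up to 0.5), 15-26% for 6 and 26-43% for 12. The first two ranges describe the one-site design that section 3 shows. The third needs both sites and a separate test at each time. All three rest on 5% two-sided per test, any single success counting, and the assumed correlations in the working. They would fall if the sponsor adopted a joint test over times or required both outcomes to succeed.

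**What to change.** Before unblinding, state the alpha and its sidedness and name one primary contrast: for example, IFG tDCS against sham on one item type at one stated time. The sponsor should choose the item type and time to fit its objective, since Primary Objective 1 concerns duration as well as immediate gain. The 75% power then applies to that contrast, at the two-sided 5% level it was evidently computed for.

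Test the remaining outcome, site and time contrasts either in a fixed order after the primary, or with a maximum-statistic version of the permutation test already planned. Permuting each patient's labels for all outcomes and times together keeps their correlation, so the threshold is less severe than Bonferroni. If SMG is not implemented, its contrasts drop out. Say also whether the three times are tested jointly or one by one.

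The cost is wording in section 6. No treatment, visit or sample size changes. The downside is a higher threshold for the secondary contrasts or, in a fixed order, no formal claim after the first failure.
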